4.2.1 Protocol Completion/Sample Destruction

Once primary research objectives for the protocol are achieved, intramural researchers can request access to remaining samples, provided they have an IRB-approved protocol and patient consent.

Samples and associated data will be stored permanently unless the patient withdraws consent. If the patient withdraws consent the participant's data will be excluded from future distributions, but data that have already been distributed for approved research use will not be able to be retrieved. The NCI PI will report destroyed samples to the IRB if samples become unsalvageable or destroyed by environmental conditions (ex. broken freezer or lack of dry ice in shipping container) or if a patient chooses to withdraw his/her consent. Samples will also be reported as lost if they are lost in transit or misplaced by a researcher. Freezer problems, lost samples or other problems associated with samples will also be reported to the IRB, the NCI Clinical Director, and the office of the CCR, NCI.

5 SUPPORTIVE CARE

For both the administration of PROSTVAC, antiemetics, stool softeners and antidiarrheal agents may be administered as required, but are not anticipated to be needed and should not be used prophylactically on the first cycle. The selection of the specific antiemetic regimen is at the discretion of the treating physician. Antiemetic regimens will not include steroids.

Other supportive care with blood components, antibiotics, analgesics, general medical therapy, etc., will be delivered as required. Any patients taking antibiotics for any reason must complete that course of therapy and be free of evidence of further infection before receiving any dose of vaccine.

Symptomatic anemia should be treated with appropriate red blood cell or erythropoietin support. Thrombocytopenia should be treated conservatively. In the absence of bleeding or a planned invasive procedure, platelet transfusions should be given for a platelet count below 10,000/mm³. If invasive procedures are planned or the patient develops bleeding, platelet transfusions should be administered in accordance with the standard of practice, usually maintaining a platelet count of > 50,000/mm³.

Any evidence of disseminated intravascular coagulation (DIC), hemolytic uremic syndrome (HUS), or thrombotic thrombocytopenic purpura (TTP) including thrombocytopenia, hemolytic anemia, renal failure, fever or neurologic changes should be thoroughly evaluated and closely monitored and supported as clinically indicated.

5.1 EXCLUDED MEDICATIONS

While patients on protocol treatment, all medications required for the health of the patient are allowed with the following exceptions:

- Concurrent chemotherapy
- Concurrent radiation therapy
- Concurrent immunotherapy
- Concurrent anti-cancer radionuclides
- Concurrent systemic corticosteroid use (daily or every other day for continued use **> 14 days**; See section [3.6](#))
- Concomitant use of secondary hormonal treatments

5.2 TREATMENT OF VACCINIA VACCINATION COMPLICATION

5.2.1 Vaccinia Immune Globulin:

First-line treatment of some of the complications of vaccinia caused by dissemination of vaccinia virus (severe cases of inadvertent inoculation involving extensive lesions or if comorbid conditions exist, severe cases of generalized vaccinia in patients that are systemically ill and whose condition might be toxic or who have serious underlying immunosuppressive illnesses, eczema vaccinatum, and progressive vaccinia) is with VIG.

VIG is contraindicated, however, for the treatment of isolated vaccinia keratitis. VIG is a sterile solution of the immunoglobulin fraction of pooled plasma from individuals inoculated with vaccinia vaccine. VIG is an investigational agent available through the CDC's Strategic National Pharmaceutical Stockpile under an IND protocol by contacting the CDC's Smallpox Vaccine Adverse Events Clinician Information Line at [name]. Upon receipt of a call from a patient or upon direct observation of a patient or contact who manifests signs and symptoms of any of the above conditions, the investigator should place a call to the CDC as soon as possible:

- 1) to initiate review of the clinical case,
- 2) to seek consultation on the appropriateness of VIG therapy,
- 3) to determine the appropriate VIG dose and dosing method for administration, if VIG therapy is required, and
- 4) to determine how to access and have the appropriate doses of VIG delivered.

Early institution of VIG therapy is advised following recognition of clinical symptoms compatible with some vaccinia complications (eczema vaccinatum, severe generalized vaccinia, progressive vaccinia, and some cases of inadvertent inoculation). The effectiveness of VIG therapy appears to be time dependent. VIG has not proven to be of benefit in the treatment of post-vaccinia encephalitis, and is contraindicated for treatment of isolated vaccinia keratitis due to the increased risk of corneal scarring.

A new intravenous formulation of VIG is available through the CDC, which has a lower level of aggregated protein, allowing it to be used by either the IM or IV route. This formulation will

most likely be preferred for administration and investigators will be instructed by the CDC regarding appropriate dosing and method of administration based on formulation and availability. There is no guarantee that VIG will successfully treat complications. At present, there are no other anti-viral therapies of proven benefit for the treatment of vaccinia-related complications.

5.2.2 Cidofovir (Vistide®, Gilead Sciences):

Cidofovir is an FDA-approved antiviral drug for the treatment of CMV retinitis among patients with AIDS. Cell-based in vitro studies and animal model studies have demonstrated antiviral activity of this agent against certain orthopoxviruses. Currently, efficacy in the treatment of vaccinia-related complications in humans is unknown. According to the CDC, “VIG is recommended as first line of therapy. Cidofovir may be considered as a secondary treatment, and will only be released by the CDC after all inventories of VIG have been exhausted, after a patient fails to improve with VIG treatment, or as a last effort for a patient who is otherwise near death.” [Medical Management of Smallpox (Vaccinia) Vaccine Adverse Reactions: Vaccinia Immune Globulin and Cidofovir. Last updated February 11, 2003. Available at: <http://www.bt.cdc.gov/agent/smallpox/vaccination/mgmt-adv-reactions.asp>].

6 DATA COLLECTION AND EVALUATION

6.1 DATA COLLECTION

Eligible patients must be confirmed and checklist completed. Consent form must be signed prior to registration with Central Registration Information Services.

Data will be secured in NCI C3D database. Data will be collected using protocol-specific case report forms, and verified for accuracy and completeness. Hard copies of data will be stored in locked secured areas and data will be entered onto a secured electronic data base. The following protocol-specific study forms will be complete and stored: eligibility checklist (developed by Central Registration Office, CRO). A copy of all serious AE forms will be kept in the research record.

- 6.1.1 Treatment is given according to protocol (dated notes about doses given, complications, and clinical outcomes).**
- 6.1.2 Toxicity is assessed according to protocol (laboratory report slips, etc.)**
- 6.1.3 Response is assessed according to protocol (X-ray, scan, lab reports, and date noted on clinical assessment, as appropriate).**
- 6.1.4 Drug Accountability Records are kept for each patient.**

The PI at each site will be responsible for overseeing entry of data into an in-house password protected electronic system (C3D) and ensuring data accuracy, consistency and timeliness. The principal investigator, associate investigators/research nurses and/or a contracted data manager will assist with the data management efforts. All data obtained during the conduct of the protocol will be kept in secure network drives or in approved alternative sites that comply with NIH

security standards. Primary and final analyzed data will have identifiers so that research data can be attributed to an individual human subject participant.

All adverse events, including clinically significant abnormal findings on laboratory evaluations, regardless of severity, will be followed until return to baseline or stabilization of event. Patients will be followed for adverse events for at least 30 days after removal from study treatment or until off-study, whichever comes first.

An abnormal laboratory value will be recorded in the database as an AE **only** if the laboratory abnormality is characterized by any of the following:

- Results in discontinuation from the study
- Is associated with clinical signs or symptoms
- Requires treatment or any other therapeutic intervention
- Is associated with death or another serious adverse event, including hospitalization.
- Is judged by the Investigator to be of significant clinical impact
- If any abnormal laboratory result is considered clinically significant, the investigator will provide details about the action taken with respect to the test drug and about the patient's outcome.

End of study procedures: Data will be stored according to HHS, FDA regulations, and NIH Intramural Records Retention Schedule as applicable.

Loss or destruction of data: Should we become aware that a major breach in our plan to protect subject confidentiality and trial data has occurred, the IRB will be notified.

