3.3 TREATMENT MODIFICATIONS

3.3.1 Vaccine

3.3.1.1 Dosing delay

- Patients must have recovered to \leq grade 1 toxicity related to vaccine (or baseline) for the parameters used to assess levels of organ function required for eligibility (see Section 2.1) after each vaccination in order to receive a subsequent vaccination.
- If \geq grade 2 nonautoimmune toxicity attributable to the vaccine persists for > 42 days, the patient will not receive further vaccine inoculations and will be removed from the protocol treatment and followed for resolution of toxicity and immune endpoints.
- Patients who develop grade 3 injection site reactions will have their vaccine held until injection site reaction resolves to grade 2 or less.
- Patients who develop \geq a grade 2 allergic or autoimmune disease that threatens vital organ function or any \geq grade 3 autoimmunity, not related to a therapeutic response, will be removed from the protocol treatment and followed for resolution of toxicity and immune endpoints.
- Patients who develop any grade 4 toxicity attributable to the study drug(s) will be removed from the protocol treatment and followed for resolution of toxicity and immune endpoints.
- If a scheduled vaccine dose is missed due to scheduling or logistical issues, the vaccine may be given within 14 days of the appointed time

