7.2.2 NCI-IRB Requirements for PI Reporting at Continuing Review

The NCI PI will report to the NCI-IRB:

1. A summary of all protocol deviations in a tabular format to include the date the deviation occurred, a brief description of the deviation and any corrective action.
2. A summary of any instances of non-compliance
3. A tabular summary of the following adverse events:
 - All Grade 2 **unexpected** events that are possibly, probably or definitely related to the research;
 - All Grade 3 and 4 events that are possibly, probably or definitely related to the research;
 - All Grade 5 events regardless of attribution;
 - All Serious Events regardless of attribution.

NOTE: Grade 1 events are not required to be reported.

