8.1.1 Halting Rules

The study will be halted for review of changes to the protocol and consent if either of the following is met:

- One occurrence of grade 5 toxicity attributed to the treatment regimen.
- Two occurrences of grade 4 toxicity attributed to the treatment regimen.

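### The criteria in section 6.1 for recording a laboratory abnormality as an adverse event omit CTCAE grade, vaccine delay and removal from treatment, so they are narrower than the IRB toxicity table and the grade-based safety rules

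*Combined protocol and SAP*

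**What the plan says.** In section 6.1 (the text under 6.1.4) the protocol states that "An abnormal laboratory value will be recorded in the database as an AE" only if at least one listed criterion applies. Four are fixed. The first reads "Results in discontinuation from the study". The other three are that the value comes with signs or symptoms, that it has to be treated, and that it is linked to a death or a further serious event. The fifth is discretionary: the investigator judges the value to have significant clinical impact. A further line asks that, for any result thought clinically significant, the investigator describe what was done about the study drug and how the patient fared.

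Other sections work on CTCAE grade:

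- Section 3.3.1.1 holds the next vaccination until vaccine-related toxicity in the organ-function parameters used for eligibility is back to grade 1 or baseline. In 2.1.1.8 and 2.1.1.9 those parameters are granulocytes, platelets, haemoglobin, bilirubin, AST and ALT.
- Section 3.3.1.1 also states: "Patients who develop any grade 4 toxicity attributable to the study drug(s) will be removed from the protocol treatment". Section 3.7.1 has a parallel rule for grade 4 toxicity that is at least possibly related.
- Sections 3.1.1 and 8.1.1 list as a halting event: "Two occurrences of grade 4 toxicity attributed to the treatment regimen".
- Section 7.2.2 requires a table at continuing review that includes "All Grade 3 and 4 events that are possibly, probably or definitely related to the research".

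Section 7.1.1 defines an adverse event to include an abnormal laboratory finding, with no condition on symptoms or treatment.

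**The concern.** The recording rule and the rules that use the record are built on different things. Section 6.1 asks what the laboratory value did to the patient or what was done about it clinically. Sections 7.2.2, 3.3.1.1, 3.7.1, 3.1.1 and 8.1.1 ask what grade it was and whether it was related. A related value can therefore be grade 3, delay the vaccine and belong in the IRB table without meeting any fixed criterion in 6.1.

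What is at stake is the completeness of the toxicity summary, above all for the haematological and hepatic parameters that Appendix C has drawn at the vaccination visits. If sites use the discretionary criterion differently, the laboratory toxicity reported will partly reflect site habit.

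**Working it through.** The documents state no figure on this point, so the check sets the sections side by side.

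**1. Does removal from vaccine count as discontinuation from the study?** Sections 3.7.1 (removal from protocol therapy) and 3.7.2 (off study) are separate lists, and 3.7.3 requires separate notices for the two. Being off treatment appears in 3.7.2 only in combination with agreement to be followed on another protocol. Section 3.3.1.1 keeps a man removed for grade 4 toxicity under follow-up for resolution and immune endpoints. On a plain reading, removal from vaccine does not by itself meet the first criterion.

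**2. Take three asymptomatic, untreated, vaccine-related laboratory values in a man who stays on study.** Each fails the four fixed criteria.

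| Value | What the protocol makes of it | Route into the adverse event record under 6.1 |
|---|---|---|
| Grade 2 in an eligibility parameter, above baseline grade | Next vaccination delayed (3.3.1.1) | Investigator's judgement only |
| Grade 3 in an eligibility parameter | Delay (3.3.1.1); belongs in the IRB table (7.2.2) | Investigator's judgement only |
| Grade 4 | Removal (3.3.1.1, 3.7.1); IRB table (7.2.2); counts towards halting (3.1.1, 8.1.1) | Investigator's judgement only |

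**3. How likely is it that the judgement lets the value through unrecorded?** For grade 4, the investigator would have to attribute the value to vaccine, stop the vaccine permanently because of it, and still hold that it lacked significant clinical impact. The text allows that, but it is unlikely. For grade 3, or for a value that only delays a dose and then resolves, the same judgement is much easier to make.

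**4. What other trace would exist?**

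- *Removal from therapy:* the Central Registration Office must be told (3.7.3). Participating sites send the form to the NCI study coordinator (3.7.3.1). A grade 4 value therefore leaves a central trace.
- *Dose delay:* no equivalent central notice is described.
- *Laboratory results:* these exist either way, and 6.1.2 has toxicity assessed from laboratory reports. A laboratory result is not itself a graded, attributed adverse event entry.
- *Team review (7.7.1):* weekly at the NCI clinic and every 6 weeks by call with the participating sites. It is described as a review of adverse events.

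**5. Which uses depend on the adverse event record?** The table in 7.2.2 is expressly a summary of adverse events, so it depends directly. The halting rule is worded as a count of toxicities, so it depends only so far as the record supplies the information in practice.

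**6. Can a size be given?** It would need the rate of related grade 3 and 4 laboratory toxicity, the share that is asymptomatic and untreated, and the share of those left unrecorded. None of the three is in the documents, so no number is offered.

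**The case against.** **The discretionary criterion already covers this.** A conscientious investigator would record most such values, and 6.1 contemplates laboratory findings that lead to action on the study drug. This stands as a reason to think grade 4 omissions rare. It does not remove the mismatch, because nothing ties that judgement to grade or to a change in vaccination.

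**The halting rule does not run on the adverse event database.** This stands. A reader might infer that 6.1 as written causes the halting rule to miss grade 4 events. The documents do not support that: 3.1.1 and 8.1.1 count toxicities, 6.1.2 uses laboratory reports, and removal from therapy is notified centrally.

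**Discontinuation from the study could be read to include stopping treatment.** Section 6.2.1.1 pairs the two when hormonal therapy is started. The ambiguity is real, but 3.7.1 to 3.7.3 separate them, and the looser reading would still leave out dose delays.

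**Section 7.2.2 may mean only adverse events as recorded under 6.1.** Limiting which laboratory values are entered is a legitimate way to reduce noise. But 7.2.2 speaks of all related grade 3 and 4 events, and 7.1.1 counts an abnormal laboratory finding as an adverse event. If the narrower meaning is intended, the protocol does not say so.

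**The vaccine is described as well tolerated.** Sections 1.2.3 and 10.4 do say this, so the number of affected events may be small.

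**Conclusion.** The inconsistency is real and modest. The recording rule in 6.1 is narrower than 7.2.2 and than the grade-based rules in 3.3.1.1, 3.7.1, 3.1.1 and 8.1.1. Its firmest effect is on asymptomatic, untreated, related grade 3 values and on values that delay a dose, which enter the record only at the investigator's discretion. The IRB table can therefore be incomplete. Omission of a grade 4 value is possible but less likely. An under-count for halting is possible but not shown.

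The conclusion rests on reading discontinuation from the study as distinct from removal from therapy, as 3.7 does, and on the list in 6.1 being exclusive, as its wording says. It assumes no event rate.

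**What to change.** Reconcile 6.1 with 7.2.2, 3.3.1.1, 3.7.1 and 8.1.1 by adding two criteria to the 6.1 list:

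- the value results in a delay of vaccine or in removal from protocol treatment;
- the value is CTCAE grade 3 or higher and at least possibly related to PROSTVAC.

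Grade the values from the laboratory results already collected. Add one sentence saying that attributable grade 4 toxicities recorded this way feed the existing count in 3.1.1 and 8.1.1. Section 7.2.2 also lists unexpected related grade 2 events. The two criteria catch those only if they delay or end vaccination, so the sponsor should say whether the others are meant to be recorded.

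This changes recording only. No dose, delay, removal or halting rule is altered, and no new reporting deadline is needed. The cost is two bullets and a sentence in an amendment, and slightly more adverse event entries.

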6.2 RESPONSE CRITERIA

Patients will not undergo scheduled radiographic assessment for metastatic disease unless clinically indicated for increasing PSA or symptoms.

6.2.1 Disease Progression

6.2.1.1 PSA will not be used to measure progression of disease. Patients will be offered androgen deprivation therapy (ADT) as clinically indicated. Starting ADT will be done at the discretion of the investigator, although this will result in treatment termination and removal from the clinical trial. Patients may go on ADT at any time, although this may result in removal from the trial. PSA will be used to calculate PSA kinetics/tumor growth kinetics.

6.2.1.2 Development of a new bone lesion on bone scan.

6.2.1.3 Development of a soft tissue mass, identified on CT scan or physical exam, consistent with metastatic prostate cancer. If identified on physical exam, the lesion may be biopsied to confirm the presence of prostate cancer.

6.2.1.4 Development of urethral, ureteral, or spinal cord obstruction secondary to tumor.

- 6.2.1.5 Development of cytologically positive pleural effusion or lymphangitic spread in the lungs.
- 6.2.1.6 Symptoms which in the opinion of the investigator are consistent with clinical progression.

6.3 TOXICITY CRITERIA

The following adverse event management guidelines are intended to ensure the safety of each patient while on the study. The descriptions and grading scales found in the revised NCI Common Terminology Criteria for Adverse Events (CTCAE) version 4.0 will be utilized for AE reporting. All appropriate treatment areas should have access to a copy of the CTCAE version 4.0. A copy of the CTCAE version 4.0 can be downloaded from the CTEP web site (http://ctep.cancer.gov/protocolDevelopment/electronic_applications/ctc.htm#ctc_40).

7 SAFETY REPORTING REQUIREMENTS/DATA AND SAFETY MONITORING PLAN

7.1 DEFINITIONS

7.1.1 Adverse Event

Any untoward medical occurrence in a human subject, including any abnormal sign (for example, abnormal physical exam or laboratory finding), symptom, or disease, temporally associated with the subject's participation in research, whether or not considered related to the subject's participation in the research.

7.1.2 Suspected adverse reaction

Suspected adverse reaction means any adverse event for which there is a reasonable possibility that the drug caused the adverse event. For the purposes of IND safety reporting, 'reasonable possibility' means there is evidence to suggest a causal relationship between the drug and the adverse event. A suspected adverse reaction implies a lesser degree of certainty about causality than adverse reaction, which means any adverse event caused by a drug.

7.1.3 Unexpected adverse reaction

An adverse event or suspected adverse reaction is considered "unexpected" if it is not listed in the investigator brochure or is not listed at the specificity or severity that has been observed; or, if an investigator brochure is not required or available, is not consistent with the risk information described in the general investigational plan or elsewhere in the current application.

"Unexpected", also refers to adverse events or suspected adverse reactions that are mentioned in the investigator brochure as occurring with a class of drugs or as anticipated from the pharmacological properties of the drug, but are not specifically mentioned as occurring with the particular drug under investigation.

